Plasma/serum storage (for virology)		х	х					Х	Х			х		Х		Х
Adverse events		х	Х	х	Х	х	Х	Х	Х	Х	х	Х	Х	Х	Х	Х
Concomitant medications	х	Х	х	Х	Х	Х	Х	Х	Х	Х	Х	х	х	Х	Х	Х
Pregnancy test		Х	Х													

Liver biopsy to be performed between screening and baseline in a sub-set of ~20 patients, 2. Baseline to occurs 4 – 12 weeks after initial screening

PROTOCOL Version 2.0 12th Aug 2016

Sponsor Imperial College

Alternative Protocol Interferon Arm

Visit number	1	2	3	4	5	6	7	8	9	10	11	12	13	14	15	16
Week	-4	0	2	4	8	12	16	20	24	28	40	52	78	104	130	156
Interferon Group	Screening ²	Baseline	IFN week 2	IFN week 4	IFN week 8	IFN week 12	IFN week 16	Post IFN week 4	Post IFN week 8	Post IFN week 12	Post IFN week 24	Post randomisation month 12	Post randomisation Month 18	Post randomisation month 24	Post randomisation month 30	Post randomisation month 36
Consent	Х															
Demographic data	х															
Inclusion / Exclusion		х														
Randomisation		х														
Medical history	х															
Vital signs	х	х	х	х	х	х	х	х	х	х	х	Х	Х	Х	Х	Х
Physical examination	х											Х		Х		Х
Liver biopsy ¹	х															
Ultrasound/Fibroscan	х															
HBV Genotyping								х								
qHBsAg	х															
HBsAg		х		х				х				Х		Х		Х
HBV DNA	х	х	х	х	х	х	х	х	х	х	х	Х	Х	Х	Х	Х
LFTs	х	х	х	х	х	х	х	х	х	х	х	Х	Х	Х	Х	Х
Thyroid function	х			Х			х				х					
Electrolytes & creatinine	Х				Х		Х			Х		х				
Prothrombin time	х	х	х	Х	х	х	х	Х	х	х	х	Х	Х	Х	Х	Х
FBC	Х		Х	Х	Х	Х	Х	Х			х	х		Х		Х
PBMC collection (for immunology assays)		х						Х		х		х		Х		Х
Plasma/serum storage (for virology)		Х						Х		Х		х		Х		Х
Adverse events		х	Х	х	х	х	х	Х	х	х	х	Х	Х	Х	Х	Х
Concomitant medications	Х	Х	Х	Х	Х	х	Х	Х	х	Х	х	х	х	Х	Х	Х
Pregnancy test		х														

1. Liver biopsy to be performed between screening and baseline in a sub-set of ~20 patients, 2. Baseline to occurs 4 – 12 weeks after initial screening

Additional visits may be made during interferon therapy to support or instruct patients but these will not be considered as study visits and will not be recorded in the study CRF.

Additional visits may be made at the discretion of the investigator for safety monitoring if hepatitis flares occur or for other safety reasons. These will be recorded in the unscheduled visit form.

Visit windows/tole	erance.

Arm	Visit	Tolerance
Interferon Arm	2	2 weeks – 3 months
(including	3-12	+/- 3 days
alternative	13-16	+/- 10 days
interferon arms)		
Withdrawal	2	2 weeks – 3 months

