6.1 Adherence

Subjects in the Interferon arm will be monitored at visits 4,5,6,7 and 8 during the Peg-IFN treatment phase (or visits 2,4,8,12 and 16 in the alternative protocols). Adherence will be monitored by patient reporting and any dose reductions will be reported in the CRF.

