6.5 Discontinuation of Study Treatment and Withdrawal from Study

(i) Recommencement of nucleos(t)ide analogues

Retreatment with nucleos(t)ide analogue therapy will be recommenced according to the following criteria for exaggerated flares:

- 1. Disturbance of liver synthetic function
 - a. Bilirubin > 35 uMol/l
 - b. INR > 1.3
- 2. ALT > 20 x upper limit of normal
- 3. If HBV DNA and/or ALT remain persistently elevated for more than 6 months
- 4. If, in the opinion of investigator or patient there is a risk to health

It is possible that there may be variation in the criteria used to determine whether a patient with hepatitis flare post cessation would need to be restarted on treatment according to criteria number 4. Data will be collected on patients considered for retreatment to determine whether any systematic differences appear between the two groups.

Recommencement will not be considered as a withdrawal from the study. A form will be completed in the eCRF to document the date and reason for recommencement. Patients who resume nucleos(t)ide analogue therapy will be monitored at intervals at unscheduled visits until ALT, Bilirubin and INR test results begin to normalise and once they have returned to normal then the patients will return to the study visit schedule until the end of the study.

(ii) Permanent discontinuation of study treatment

Subjects may discontinue study medication for the following reasons:

- At the request of the subject.
- Adverse event/ Serious Adverse Event
- Allergic reaction to IMP
- In the event of pregnancy
- If the investigator considers that a subject's health will be compromised due to adverse events or concomitant illness that develops after entering the study.

(iii) Withdrawal from Study

Withdrawal from the study refers to discontinuation of study treatment and study procedures and can occur for the following reasons:

- Subject decision
- Loss to follow-up

In this situation the patient will be encouraged, where possible, to resume the nucleos(t)ide analogue treatment which they were taking before enrolling in the study.

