An SAE form should be completed and entered into the eCRF for all SAEs within 24 hours. This will automatically send alert emails to the Chief Investigator, the Project Manager and the Sponsor.

Safety Reporting Overview

* Unless identified in the protocol as not requiring immediate reporting

Contact details for reporting SAEs and SUSARs

Follow the study specific procedure for reporting SAEs and SUSARs and complete an SAE form & submit to the Study Coordination Centre as soon as possible (within 24 hrs). SAE forms are available on the InForm eCRF system.

E-mail: [contact]

(iii) Definition of an Adverse Reaction (AR)

All untoward and unintended responses to an IMP related to any dose administered or relating to the withdrawal of the patient from nucleos(t)ides. All AEs judged by either the reporting investigator or the sponsor as having reasonable causal relationship to a medicinal product qualify as adverse reactions. The expression reasonable causal relationship means to convey in general that there is evidence or argument to suggest a causal relationship.

Exaggerated hepatitis flares are defined according to the following criteria:

- 1. Disturbance of liver synthetic function
 - a. Bilirubin > 35 uMol/l
 - b. INR > 1.3
- 2. ALT > 20 x upper limit of normal

- 3. If HBV DNA and/or ALT remain persistently elevated for more than 6 months
- 4. If, in the opinion of investigator or patient there is a risk to health

These are an expected reaction to nucleos(t)ide withdrawal and will not be recorded or reported as an AR/AE. Exaggerated flares will be recorded in the Case Report Form to monitor patient safety throughout the trial as described elsewhere in the protocol.

Expected non-serious side effects of interferon (as documented in the SMPC) will not be recorded as adverse reactions.

(iv) Definition of a Serious Adverse Reaction (SAR)

A SAR is defined as a SAE that is judged to be related to any dose of study drug administered to the subject or withdrawn from the subject.

(v) Definition of Suspected Unexpected Serious Adverse Reaction (SUSAR)

Any SAR that is NOT consistent with the applicable product information as set out in the Investigator Brochure (IB) or Summary of Product Characteristics (SPC) ie is unexpected.

An unexpected reaction to nucleos(t)ide withdrawal is defined as one which has temporal or biological relationship to the intervention but does not include a hepatitis flare.

(vi) Reporting of SUSARs

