8.2 Data Analysis

(i) Primary Endpoint Analysis

This analysis will be performed primarily on an intention to treat (ITT) basis. The ITT population will be all subjects who have been randomized. Secondarily, a per protocol analysis will be performed. The per protocol population will be those confirmed to be eligible who have not resumed nucleos(t)ide analogues for patient/ physician preference and those, in the interferon arm, who have completed at least 8 weeks of interferon therapy. Rates of HBsAg loss will be compared between the two groups using logistic regression adjusting for the stratification factors HBsAg titre and centre. Results will be presented as odds ratios and their 95% confidence intervals.

(ii) Secondary outcomes

Secondary outcomes to be compared between the two groups will include the primary outcome assessed at one year and at two years from baseline. Kaplan-Meier plots will be produced to show the persistence of HBsAg. The plots will be supported by formal secondary analyses using Cox proportional hazards model methods

Achievement of the inactive carrier state (defined above) will be analysed using the same procedures as the primary outcome. A statistical analysis plan will be developed and approved by the Trial Steering committee prior to any regular analysis for reports to the Data Monitoring Committee. This plan will include details of the statistical methods to be used to analyse the outcomes, and describe the methods to undertake sensitivity analyses for handling missing data. The plan will contain conform with the Clinical Trials Unit standard operating procedures

(iii) Predictors of HBsAg Loss

Predictive factors for HBsAg loss will be explored using univariate and multivariate logistic regression analysis. Separate models will be fitted for the following variables: gender, age, duration of antiviral therapy, viral genotype, viral load pre-treatment, HBsAg titre, centre, peak ALT value post withdrawal, peak viral load post withdrawal, hepatic cccDNA, number of infected hepatocytes and ELISPOT counts. Odds ratios and their 95% confidence intervals produced from each of the models will be presented. Following this, a multivariate logistic regression analysis will be performed will include the variables that were statistically significant in the univariate analysis plus a variable for treatment group.

(iv) Safety analysis

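### Section 6.1 gives week numbers as visit numbers for adherence in the alternative protocols; as a lesser point, the 8-week per-protocol condition applies to one arm only and 'preference' is undefined

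*Protocol*

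**What the plan says.** **Adherence.** Protocol 6.1 monitors interferon adherence by patient report at visits 4 to 8 in the standard interferon arm, "or visits 2,4,8,12 and 16 in the alternative protocols". Section 2.4 lists adherence as a safety endpoint. Section 9.1.3 relies on 6.1 for recording it and waives drug accountability records. The visit table headed "Alternative Protocol Interferon Arm" in 5.3 numbers the visits for the alternative protocols.

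**Per-protocol set.** Section 8.2(i) makes intention to treat on all randomised patients primary, and then says: "Secondarily, a per protocol analysis will be performed". The set is eligible patients "who have not resumed nucleos(t)ide analogues for patient/ physician preference and those, in the interferon arm, who have completed at least 8 weeks" of interferon.

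**Restart.** Section 6.5(i) says "Retreatment with nucleos(t)ide analogue therapy will be recommenced according to the following criteria for exaggerated flares". Criteria 1 to 3 are laboratory-based. Criterion 4 reads "If, in the opinion of investigator or patient there is a risk to health". Section 7.4(iii) repeats the list under "Exaggerated hepatitis flares are defined according to the following criteria". Section 6.5(i) adds "Recommencement will not be considered as a withdrawal from the study", and has the date and reason for each restart entered on an eCRF form.

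**The concern.** Two things looked wrong.

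(a) The adherence visits in 6.1 do not match the schedule they refer to. If the pilot triggers an alternative protocol and sites follow 6.1 literally, most adherence reports would be taken before any exposure or after interferon has ended. An endpoint, and the input to the 8-week condition, would then rest on thin or retrospective data.

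(b) The 8-week condition is applied after randomisation and in one arm only. In the main design both arms stop analogues at week 0 and interferon starts at week 4, so 8 weeks of interferon is reached at week 12. A control patient who meets an objective flare criterion and restarts analogues before week 12 stays in the set. An interferon patient with the same event leaves it if interferon was never started or was stopped before 8 weeks. The per-protocol comparison is therefore not like for like. In addition, the patient or physician preference that 8.2(i) uses to exclude restarts is not defined against the restart criteria in 6.5(i).

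**Working it through.** **(a) Visit numbers against weeks, from the alternative schedule in 5.3**

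| Visit named in 6.1 | What 5.3 places there |
|---|---|
| 2 | week 0, baseline |
| 4 | week 4, interferon week 4 |
| 8 | week 20, 4 weeks after interferon |
| 12 | week 52, month 12 |
| 16 | week 156, month 36 |

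In the same table, interferon weeks 2, 4, 8, 12 and 16 are visits 3, 4, 5, 6 and 7. The list in 6.1 equals those week numbers exactly, so weeks were written as visits. The list for the standard arm is right: visits 4 to 8 are weeks 6, 8, 12, 16 and 20, which is interferon weeks 2, 4, 8, 12 and 16 after the 4-week gap. Of the five visits named for the alternative protocols, only visit 4 can report adherence during treatment. Interferon week 8, the point that decides per-protocol membership, is visit 5 and is not on the list.

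**(b) Size of the one-sided exclusion**

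The plan gives no figure for the per-protocol set. Its sample size is not affected, and it reproduces with a two-sided 5% test, pooled variance and no continuity correction: n = [1.96 × √(2 × 0.3 × 0.7) + 1.2816 × √(0.16 + 0.24)]² / 0.20² = 108.2, hence 109 per arm.

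Inputs from the protocol: 20% loss of HBsAg at 3 years in the control arm (8.1), 120 per arm (8.1), interferon adherence over 95% (section 5). Assumptions: no true effect, so 20% in both arms; a fraction f of the interferon arm is removed; those removed lose HBsAg at rate r; the control arm stays whole. The protocol gives neither f nor r. Adherence over 95% suggests f of about 5% or less, if non-adherence is taken to mean missing the 8 weeks.

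Interferon per-protocol rate p = (0.20 − f × r)/(1 − f). Odds ratio = [p/(1 − p)]/0.25. Rejection is the two-sided chance of p < 0.05 by normal approximation, with 120 × (1 − f) against 120 patients.

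| f | r | p | Odds ratio | Rejection |
|---|---|---|---|---|
| 5% | 0% | 21.1% | 1.07 | 5.5% |
| 5% | 30% | 19.5% | 0.97 | 5.1% |
| 10% | 0% | 22.2% | 1.14 | 7.0% |
| 10% | 30% | 18.9% | 0.93 | 5.5% |
| 20% | 0% | 25.0% | 1.33 | 14.4% |
| 20% | 30% | 17.5% | 0.85 | 7.4% |

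Example: f = 5%, r = 0 gives 0.20/0.95 = 0.2105 and 0.2105/0.7895/0.25 = 1.07. With f = 5% and r = 35%, p = (0.20 − 0.0175)/0.95 = 19.2% and the odds ratio is 0.95. Whenever r = 20% the odds ratio is 1.00.

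**(c) Preference against criterion 4**

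Section 8.2(i) excludes restarts for preference in both arms. The nearest item in 6.5(i) is criterion 4, which requires a perceived risk to health. The protocol does not say whether preference means criterion 4 restarts, or restarts outside all four criteria.

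**The case against.** The case against is strong on (b) and weak on (a).

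- A minimum-exposure rule in the only arm that receives the drug is a common per-protocol convention, and the intention-to-treat primary analysis guards against its known bias. This stands, and it limits (b) to a labelling point.
- A reader might infer that an interferon patient who flares and restarts early is always removed. The protocol does not support this. Nothing in it says interferon stops when analogues restart, and 6.5(ii) does not name a flare or restart as a reason to stop study medication. Removal follows only if interferon was never started or was stopped before 8 weeks. Likewise, if criterion 4 restarts count as preference, control patients who restart under criterion 4 are removed too, so retention of controls is certain only for objective-criterion restarts.
- A reader might infer that 6.5 classes preference restarts as flares, so that 8.2 contradicts it. It does not: criterion 4 is about risk to health, not preference. The word is undefined, and the exclusion covers both arms, so by itself it creates no imbalance. In an open-label trial its use could still differ by arm. Section 6.5(i) foresees varying use of criterion 4 and collects data to check for differences between the groups.
- On (a), the visits themselves are correctly scheduled in 5.3, the alternative protocols are contingent on the pilot, and a later visit could ask about earlier doses. It would therefore be too strong to say that interferon completion would go unchecked. The contradiction between 6.1 and 5.3 remains.

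**Conclusion.** The point holds in two parts of unequal weight.

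(a) Section 6.1 is wrong as written for the alternative protocols. One of its five visits can give on-treatment adherence, and the interferon week 8 visit is missing from the list. This rests only on the two sections and needs no assumption. It matters only if an alternative protocol is used.

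(b) The 8-week condition makes the per-protocol comparison unequal, but the effect is small at the protocol's own adherence figure: an odds ratio of about 0.95 to 1.07 under no true effect with 5% removed and r between 0 and 35%. It grows if more patients are removed early (0.85 to 1.33 at 20% removed and r between 0 and 30%), and its direction depends on r, which is unknown. The retreatment figure of up to 45% in section 5 is not confined to the period before 8 weeks of interferon, so it does not estimate f. The primary analysis and the sample size are unaffected.

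The undefined preference term is an ambiguity to settle, not a contradiction.

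**What to change.** 1. In 6.1, reconcile the alternative-protocol visits with 5.3: visits 3, 4, 5, 6 and 7 (weeks 2, 4, 8, 12 and 16), tied to the alternative interferon schedule.
2. In 8.2(i), label the per-protocol result as supportive and note that its exposure condition applies to one arm only.
3. In 8.2(i), define the preference exclusion by reference to criteria 1 to 4 in 6.5(i), saying explicitly whether criterion 4 restarts are kept or excluded. Use the restart reason already on the eCRF form.

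The cost is wording only, with no new data.

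Two further remedies may suggest themselves, and neither works. A common rule that nobody may have restarted by week 12 would keep the interferon-only exposure condition and exclude patients who restarted as the protocol directs. It also has no meaning for a combined-treatment arm, which takes analogues until week 16 and so has only just stopped or not yet stopped them. Defining preference as none of criteria 1 to 3 being met on restart-visit laboratory values fails because criterion 3 needs more than 6 months of results, and it would turn every restart made on criterion 4 alone into a preference restart.

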3.2 Design

The main trial for NUC-B will be performed in at least 10 sites in England. It is a randomised, open-label, multicentre trial comparing nucleoside / nucleotide analogue withdrawal against nucleoside/ nucleotide analogue withdrawal followed by a 16 week course of pegylated interferon in HBeAg-negative chronic hepatitis B virus infected patients. Patients will be followed for 3 years after randomisation.

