5.2 Randomisation

Patients will be electronically randomised using the InForm eCRF online custom built database to the two management arms in equal proportions using variable block sizes. Randomisation will be stratified by gender and by HBsAg titre at baseline (< or \ge 2000 IU/mI) as this is the strongest predictor of clinical outcome in interferon based treatment and was found to be a predictor of outcome in the Hadziyannis study.

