5.6 Laboratory Evaluations

(i) Haematology

Full blood counts and prothrombin times will be measured using standard methods in the routine haematology department at each participating site.

(ii) Biochemistry

Liver function tests (bilirubin, albumin, ALT, alkaline phosphatase), thyroid function tests (TSH & T4), glucose, electrolytes and creatinine will be measured using standard methods in the routine haematology department at each participating site.

(iii) HBV DNA

HBV DNA will be measured quantitatively using real-time PCR based assays in the routine virology departments at each participating site. Results will be reported back on the eCRF.

(iv) HBV genotype

Plasma from an EDTA specimen taken at week 4 will be collected and processed at each participating site and stored at -80°C until transported to Virology at UCLH. Genotyping will be performed by sequence analysis of the HBV DNA.

(v) HBsAg quantification

A quantitative HBsAg measure will be performed at each local hospital on a screening visit blood sample. The result will be used for stratification in the randomisation system.

HBsAg concentrations will be performed using the Abbott Architect qHBsAg system in [name] laboratory. Serum samples will be collected in the virology department at each participating site and stored at -80°C until transported, frozen, in batches to Virology at UCLH.

(vi) Liver Biopsy

In patients who consent to have a liver biopsy as part of the study the procedure will be performed by a trained hepatologist or radiologist and two passes will be made with the biopsy needle to obtain 2 liver specimens of 1.5 - 2 cm in length. One of these will be placed in to 10% formaldehyde and sent to the histology laboratory for paraffin embedding and sectioning. The first 2 sections will be used for standard H&E and pico-sirius red staining to assess necroinflammatory and fibrosis scores. Two sections will be used for immunohistochemistry staining for HBsAg and HBV core antigens. Two sections will be sent to [name] laboratory for measurement of cccDNA.

The second liver specimen will be collected in sterile PBS and sent by courier to [name] laboratory.

(vii) ELISPOT

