8 STATISTICAL ANALYSES

8.1 Sample Size and power considerations

HBsAg loss is the primary endpoint; the trial will compare the rate of HBsAg loss in patients three years after cessation of nucleos(t)ide analogues with the rate of HBsAg loss in patients treated with pegylated interferon after cessation of nucleos(t)ide analogues. Only one published study provides an estimate of the rate of HBsAg loss in patients who stopped treatment after 4 years of nucleos(t)ide analogues which was 10% at 1 year,18% at 2 years and 24% at 3 years. A similar study reported by Berg (EASL 2015) confirmed the 10% HBsAg loss reported at 1 year. In the present study we will recruit some patients who have had treatment with nucleos(t)ide analogues for only 3 years and we will therefore use a conservative assumption for the rate of HBsAg loss in this group at 15% at 2 years and 20% at 3 years.

There is no data on the rate of HBsAg loss in patients who have been treated with nucleos(t)ide analogues and subsequently been treated with pegylated interferon. In a trial of pegylated interferon for naïve HBeAg negative hepatitis infection 42.4% had lost HBsAg at the end of follow up if the level of HBV DNA had been <70 IU/ml at the end of treatment. As this is an exploratory study we have assumed that the rate of HBsAg loss in this group will be 30% at 2 years and 40% at 3 years. This increment would represent the very significant clinical benefit which would justify the use of interferon (with associated side effects) in this group of patients.

A trial with 90% power to detect a difference in HBsAg loss between these groups (40% vs 20%) at the P < 0.05 threshold would require 109 subjects in each arm. Therefore allowing for ~10% withdrawal / dropout in each arm we will aim to recruit 120 subjects to each arm; a total of 240 patients in total. If either arm is discontinued after the pilot, then there will still be at least 80% power in comparison with an alternative trial arm in the post pilot participants.

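### The primary model's listed stratification factors (HBsAg titre, centre) do not match those used at randomisation (gender, HBsAg titre), and the two lists must be reconciled

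*Protocol*

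**What the plan says.** Section 5.2 (Randomisation) states: "Randomisation will be stratified by gender and by HBsAg titre at baseline", with the titre cut at 2000 IU/ml. Allocation is "to the two management arms in equal proportions using variable block sizes". Centre is not mentioned there. Section 5.6(v) adds that a local quantitative HBsAg on the screening sample supplies the titre: "The result will be used for stratification in the randomisation system".

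Section 8.2(i) (Primary Endpoint Analysis) specifies the comparison of the arms: "Rates of HBsAg loss will be compared between the two groups using logistic regression adjusting for the stratification factors HBsAg titre and centre". The effect is reported as an odds ratio with its 95% confidence interval. Gender is not mentioned there. Section 8.2(ii) analyses the inactive carrier state in the same way as the primary outcome. Gender and centre appear together only in section 8.2(iii), as candidate predictors in exploratory models.

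On the number of centres, section 3.2 says: "The main trial for NUC-B will be performed in at least 10 sites in England". No maximum number of sites and no site size is given.

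**The concern.** Section 8.2 claims to name the stratification factors, yet it shares only one of two with section 5.2. An analyst who follows section 8.2 to the letter leaves out a factor that section 5.2 says was balanced by design. One who adjusts for the factors in section 5.2 departs from the stated primary model. In an open-label trial that choice should be settled before outcome data are seen.

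Two things are at stake. First, stratified allocation balances gender between the arms. If gender is related to HBsAg loss and the model ignores it, the standard error does not take credit for that balance and the test becomes slightly conservative. Second, the effect measure is an odds ratio, whose value depends on the covariates in the model, so the covariate list is part of what is being estimated.

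**Working it through.** **1. The two lists**

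| Factor | Stratifier in 5.2 | In the primary model, 8.2(i) |
|---|---|---|
| HBsAg titre | yes | yes |
| Gender | yes | no |
| Centre | no | yes, called a stratification factor |

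Section 5.6(v) confirms only titre, the one factor on which both sections agree, so it does not settle the conflict.

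**2. The plan's sample size.** For loss rates of 40% v 20% and 90% power, section 8.1 gives this requirement: "at the P < 0.05 threshold would require 109 subjects in each arm". With the pooled-variance formula, two-sided 5%, no continuity correction and mean rate 0.30:

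n = [1.960·√(2·0.30·0.70) + 1.282·√(0.40·0.60 + 0.20·0.80)]² / 0.20² = (1.270 + 0.811)² / 0.04 ≈ 108.2, rounded up to 109.

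This reproduces the stated figure. It does not depend on the covariates, so the correction leaves 109 (120 with dropout) unchanged.

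**3. Effect of the covariate list on power.** Simulated trials had 240 patients, 20% v 40% loss, and 1:1 blocked randomisation stratified by gender and titre, which takes section 5.2 as correct. The test was a Wald test from logistic regression with centre as a fixed effect. These inputs are assumptions and are not in the protocol: half of patients in each titre stratum, titre odds ratio 6, 35% in one gender category, gender odds ratio (OR) 1 to 3, and no true centre effect. "Uneven" means centre sizes proportional to 1, 1/2, 1/3 and so on. There were 1000 runs per row, and all models were fitted to the same data.

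| Centres | Gender OR | Titre + centre | Titre + gender | Difference (points) |
|---|---|---|---|---|
| 10 equal | 1 | 94.9% | 95.7% | 0.8 |
| 10 equal | 2 | 94.9% | 95.7% | 0.8 |
| 10 equal | 3 | 95.3% | 96.3% | 1.0 |
| 10 uneven | 1 | 94.3% | 94.4% | 0.1 |
| 10 uneven | 2 | 96.7% | 97.2% | 0.5 |
| 10 uneven | 3 | 96.2% | 96.3% | 0.1 |
| 20 uneven | 1 | 93.9% | 95.2% | 1.3 |
| 20 uneven | 2 | 93.9% | 94.9% | 1.0 |
| 20 uneven | 3 | 95.8% | 97.8% | 2.0 |

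Keeping centre and adding gender to it gains 0 to 0.7 points over titre + centre.

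A second simulation used 216 analysed patients (90% of 240), 12 unequal centres and gender OR 1 to 2. It gave 90.5–92.2% for titre + centre and 91.3–93.1% for titre + gender, a gain of 0.8 to 0.9 points at the ends of the ranges.

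**4. Type I error.** With 20% loss in both arms and 3000 runs per setting, it was 4.5–6.2% for titre + centre and 4.6–5.7% for titre + gender. The Monte Carlo standard error is √(0.05·0.95/3000) = 0.4 points.

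**5. Omitting a prognostic gender effect.** At gender OR 3, titre alone gave type I error of 4.1–4.4%, against 4.6–5.2% for titre + gender. The median odds ratio was 3.11–3.14, against a true conditional value of 3.27. Both show mild conservatism and a pull towards 1.

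**6. How sparse centre would be.** The chance that at least one centre has no events is as follows.
- 10 equal centres of 24 patients at 30% loss: 0.7²⁴ = 0.00019 per centre, about 0.2% for any.
- 20 equal centres of 12 patients: 0.7¹² = 0.0138 per centre, about 24% for any.
- 12 equal centres, 9 analysed per arm: 1 − (1 − 0.8⁹·0.6⁹)¹² ≈ 1.6%. With 20% loss in both arms, 1 − (1 − 0.8¹⁸)¹² ≈ 20%.
- 20 uneven centres (simulated, 20% v 40%): on average about 3.4 centres have no events or only events.

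**The case against.** The best defence is that adjusting for centre in a multicentre trial is legitimate whether or not it was a stratifier. Section 6.5 itself expects that clinicians may vary in when they restart nucleos(t)ide analogues, which is a plausible reason to keep it. How centre is coded is ordinary analysis-plan detail, and the practical effect is small. All of this stands. It does not answer the contradiction, because the protocol itself names the model's factors and gives centre a status that section 5.2 does not.

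A reader might infer two stronger points that the protocol does not support.

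- **That section 8.2 is the faulty section and centre was never a stratifier.** Section 5.2 may equally have left centre out. If so, removing centre from the model would drop a real stratifier.
- **That sparse centres would break the primary analysis.** Section 3.2 gives only a minimum number of sites, and at ten similar-sized sites a centre without events is very unlikely. Section 8.2 does not say that centre is a fixed effect. Even if it is, a centre with no events or only events makes its own coefficient diverge, while the treatment estimate stays finite. What remains is some upward drift of the odds ratio with many centre terms: with 20 uneven centres the median was about 3.5 against a true 3.1 at gender OR 1.

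**Conclusion.** The contradiction is real and concerns the primary model, and through it the inactive-carrier analysis. As written, the model omits a factor that section 5.2 names as a stratifier and describes as a stratifier one that section 5.2 does not name. The protocol does not show which section is in error.

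The consequence is modest: about 1 point of power, at most 2 in the settings examined, with the written model above 90% in all of them and type I error near 5%. These sizes rest on assumed titre and gender effects, assumed centre sizes and no true centre effect. The protocol gives no gender effect. The reason to act is that the primary model should be unambiguous and match the randomisation; the trial's validity is not in doubt on this account.

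**What to change.** 1. Check which factors are built into the randomisation system.
2. Make sections 5.2 and 8.2(i) name the same factors.
3. Adjust the primary model for all factors actually used in randomisation. If section 5.2 is correct, wording such as this would serve: logistic regression adjusting for the randomisation stratification factors, gender and HBsAg titre (< or ≥ 2000 IU/ml, as randomised).
4. If centre is kept without being a stratifier, call it an additional covariate and state how small centres are handled, by a random intercept or by pooling.

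The cost is one sentence in the protocol, carried into the analysis plan. Gender is needed for stratification under section 5.2, and the screening HBsAg is already measured. Adding log10 quantitative HBsAg as a continuous covariate is an optional gain in efficiency and is not part of this correction.
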